There is an urgent need for research initiatives to provide evidence regarding the safety of COVID-19 vaccines in pregnant women/individuals, the immune response they generate, and the extent of protection they provide to mothers and their newborns. The PLAN-V Study will build on the successes of the COVID-19 Ontario Pregnancy Event (COPE) Network - a collaboration of 13 obstetrical hospitals in 6 of Ontario's largest cities - to launch an in-depth study of pregnant women/individuals and their newborns.

We will recruit participants who receive the COVID-19 vaccine in pregnancy for close clinical follow-up, detailed data collection and biological sample analysis in pregnancy, at delivery and across the postpartum period. We will evaluate maternal immune responses to vaccination and examine evidence for transfer of protective antibodies to the newborn.

We have a successful track-record of research on COVID-19 infection, vaccination in pregnancy and multi-site birth cohorts. Our team includes obstetricians; maternity and newborn care specialists; virologists; infectious disease specialists; and vaccine and public health experts. This work will address key questions about COVID-19 vaccines during pregnancy that are important to Canadian families and their care providers. The PLAN-V Study is designed to fill critical knowledge gaps, and in doing so, will help inform public health recommendations, guide vaccine awareness efforts for pregnant women/individuals, and support patient counselling and informed decision-making by Canadians.

1. BACKGROUND AND RATIONALE

1.1. Background

Pregnant women/individuals are considered a high-risk population for COVID-19 infection, with higher disease severity, higher rates of hospitalization, intensive care unit admission, and death compared to non-pregnant individuals. Information related to COVID-19 vaccines in development are rapidly evolving. Pregnant women/individuals were excluded from the Phase II and Phase III vaccine trials completed to date. Therefore, there are no data on the safety of COVID-19 vaccines in this population or the effects of these vaccines in pregnancy, on the breastfed infant or on milk production.

[figure not shown]
In March 2021, the Society for Obstetricians and Gynaecologists of Canada (SOGC) re-affirmed their position that “Women who are pregnant or breastfeeding should be offered vaccination at any time during pregnancy if they are eligible and no contraindications exist”.¹ In April 2021, amid reports of alarming numbers of pregnant women in intensive care units and calls to action by maternity care providers, the Ontario Ministry of Health declared pregnant women as a high priority population for vaccination, removing previous requirements for proof of physician counselling. However, the lack of data in this population still makes it challenging for pregnant women/individuals to make informed decisions about COVID-19 vaccination during pregnancy, and for their health care providers to provide evidence-based counselling. There remains an urgent need to monitor vaccine immunogenicity and safety in this population to address critical questions about the risks and benefits for vaccination on maternal, pregnancy and longer-term child health.

1.2. Our Approach

We will build on existing resources and expertise available through the COVID-19 Ontario Pregnancy Event (COPE) Network - a collaboration of 13 obstetrical hospitals in 6 of Ontario’s largest cities - **to establish a prospective, longitudinal cohort study of pregnant women/individuals and their infants.** COPE Network sites collectively handle ~75% of in-hospital Ontario births. To-date, of the current COPE Network sites, 10 have been designated to run COVID-19 vaccine clinics and the other 3 are within proximity to a designated clinic.

We will launch an in-depth investigation of the immunogenicity of COVID-19 vaccines in pregnant women/individuals, and the role of maternal vaccination for the protection of their newborns. The study will include extensive Ontario-wide maternal and newborn bio-sampling in the prenatal, delivery and postpartum periods to address critical questions including: **(1) What is the immunogenicity of COVID-19 vaccines in this population, (2) What is the fetal/newborn immune response to maternal vaccination (3) Does timing of maternal vaccination in pregnancy affect fetal/newborn antibody transfer? (4) How durable are maternal and newborn immune responses? and (5) How do newborn immune responses differ between natural maternal COVID-19 infection in pregnancy versus maternal vaccination in pregnancy?** Our design will enable us to compile detailed longitudinal maternal-newborn clinical and immune response profiles beyond what can be accomplished from larger surveillance projects.

The framework for collaboration, participant recruitment and sample collection exist through the COPE Network infrastructure and we can rapidly operationalize this study. Since May 2020, the COPE Network has been collecting maternal and infant samples to generate complete infection and antibody profiles [CIHR-funded VR4-172760].³ To date, more than 150 SARS-CoV-2 infected participants have delivered at a COPE site, or are enrolled and pending delivery. The PLAN-V study is the natural progression of this work and will leverage existing study infrastructure to address key questions about immunogenicity of COVID-19 vaccinations in the pregnant population and the fetal/newborn immune response.

2. GOAL & OBJECTIVES

There is a pressing need for research to answer critical questions about the role of maternal vaccination for protection of the mother-infant dyad, inform public health recommendations and support evidence-based decision-making by Canadian families and their care providers.

Our goal is to generate rapid, reliable evidence specific to immunogenicity and safety of COVID-19 vaccines in the pregnant population. The specific PLAN-V Study objectives are:

1. To evaluate immunogenicity of COVID-19 vaccines in pregnant women/individuals and the fetal/newborn immune response to maternal vaccination.
2. To evaluate safety of COVID-19 vaccination in pregnant women/individuals based on obstetrical, fetal and newborn health outcomes.
3. To compare immune responses to COVID-19 vaccination and natural COVID-19 disease among pregnant women/individuals and their infants exposed *in utero*
4. To compare the immune responses to COVID-19 vaccination between pregnant and non-pregnant women/individuals.

3. METHODOLOGY

3.1. Study design and setting

PLAN-V is an Ontario-based prospective, longitudinal study that will consist of extensive biosampling and detailed data collection from pregnant women/individuals and their infants across the prenatal, delivery and postpartum periods. With this approach, we will generate detailed participant profiles that will enable us to explore vaccine reactogenicity;⁴ vaccine-associated adverse events;^{5,6} frequency of obstetrical and fetal/newborn outcomes; and measures of infant health and well-being. We will build on existing resources and expertise available through the **COVID-19 Ontario Pregnancy Event (COPE) Network** to establish a prospective, longitudinal cohort study of pregnant women/individuals, and their infants.

3.2. Study population

The PLAN-V Study will consist of **pregnant women/individuals** who are planning to receive a COVID-19 vaccine(s) at any stage in pregnancy.

3.2.1. Inclusion criteria

[figure not shown]
Participants must meet all of the following inclusion criteria at the time of enrollment to be eligible:

- Women/Individuals ≥ 16 years of age who are $\geq 7^{0/7}$ weeks' gestation on the day of enrollment
- Capacity to provide informed consent and to comprehend and comply with the study requirements
- Planning to deliver at a participating site hospital
- Planning to receive or have previously received one-dose of a Health Canada approved COVID-19 vaccine (any product, any number of doses) during the current pregnancy

Gestational age will be calculated based on the date of the first day of the self-reported last menstrual period (LMP) and corroborated by ultrasound. Early pregnancy prior to first ultrasound will be confirmed by urine pregnancy test, collected by study team at time of enrollment. Documented viable pregnancy is required prior to first vaccine, to continue in the study.

3.2.2. Exclusion criteria

Women/Individuals meeting any of the following criteria will not be eligible for participation in this study

- Cases with known major fetal concerns (e.g., major congenital malformations, chromosomal abnormalities) at the time of enrollment
- Women/Individuals who are fully vaccinated against COVID-19
- Women/Individuals who are pregnant due to surrogacy, or planning to give their child up for adoption
- Women/Individuals with a non-viable pregnancy (e.g., ectopic)

COVID-19 infection

- Women/Individuals previously infected with COVID-19 will be eligible for this study
- Women/Individuals who become infected with COVID-19 during the study period will be eligible to continue with the study protocol. COVID-19 infection (test-positive date, variant information) and symptomatology for both mother and infant (if applicable) will be documented.

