3.3. Study Exposure

The exposure of interest is COVID-19 vaccination in pregnancy. Participants will be those who receive a Health Canada approved COVID-19 vaccine (any product, any number of doses) during pregnancy.

Participants will be recruited *before* they are fully vaccinated and are pregnant with a viable fetus.

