3.4.2. Secondary Outcomes

Secondary outcomes will be those related to vaccine safety for maternal, pregnancy and newborn health.

- Secondary perinatal outcomes will include: maternal (death, non-delivery hospitalization, any infection, preterm labour, hypertensive disorders of pregnancy, placental abruption, postpartum hemorrhage), and newborn (preterm birth [<37 weeks], small-for-gestational-age [<10 th percentile for gestational age and sex-specific birth weight],⁷ fetal loss/stillbirth, term low birthweight [<2500 g], 5-minute Apgar score ≤ 5 , cord blood pH <7.0 , length of hospital stay for the birth admission, admission to neonatal ICU for >12 hours; and a composite neonatal adverse outcome indicator [NAOI], which includes congenital anomalies).^{8,9}
- Secondary postpartum outcomes will include: infant growth, frequency of infection (e.g., influenza, pneumonia, sepsis, acute respiratory infections, gastrointestinal), rates of re-hospitalization and emergency department visits during the follow-up period, and a composite indicator for pediatric complex chronic conditions namely:¹⁰ neurologic and neuromuscular; cardiovascular; respiratory; renal and urologic; gastrointestinal; hematologic or immunologic; metabolic; other congenital or genetic defect; and malignancy. Finally, we will note infant deaths at any time during the study.

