3.5.4. Study Contacts/Follow-up Schedule

Study contacts will be made at baseline, post-vaccination, delivery and across the postpartum period. The extent of data and sample collection will vary by time-point (**See Figure 2**).

- Visit 1 (V1) will occur prior to 1st dose (if applicable)
- Visit 2 (V2) will occur ≥ 14 days after 1st dose and prior to 2nd dose
- Visit 3 (V3) will occur ≥ 14 days after 2nd dose and prior to Visit 4
- Visit 4 (V4) will occur 90 days \pm 14 days after last dose
- Visit 5 (V5) will occur 180 days \pm 14 days after last dose
- **Baseline** questionnaire will occur at the time of enrollment prior to or during V2, following participant consent.
- **General follow-up** questionnaires may be completed during the study visit or completed prior to the following study visit
- **Reactogenicity questionnaire 1 (RQ1)** must be completed prior to 2nd dose
- **Reactogenicity questionnaire 2 (RQ2)** must be completed within 30 days after last dose (for single vaccine or second dose)
- **Delivery follow-up** will include secondary data collection (to reduce burden on participants during the hospital delivery admission), and sample collection.

[figure not shown]
[figure not shown]

Figure 2. Study contacts/follow-up schedule.

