3.7. Sample Collection, Shipping and Analysis

3.7.1. Sample collection

Participants will be asked to contribute biological samples. We will allow participants to choose the scope of sample collection at each time-point. Samples will include maternal blood; breastmilk/chestmilk (postpartum collection only); and newborn blood (including cord blood at delivery). (Table 2)

Sampling will be coordinated alongside routine clinical collections where possible to minimize burden to participants. If participating hospital sites have sufficient capacity and resources, participants will be given the option to (1) return to the hospital or affiliated community clinic for sample collection/drop-off; (2) schedule a home visit with a research nurse/coordinator for sample collection/pick-up; (3) mail-in samples, if dried blood spot is preferred by the participant.

For the protection of all parties, both the Site Investigator/Delegate conducting the appointment and the participant will be directed to answer a series of self-assessment questions to assess likelihood or risk of COVID-19 infection before attending in-person visits.

[figure not shown]

Table 2. Sample collection schedule for vaccinated participants

	Visit 1	Post-vaccination Follow-up ³				Delivery
		Visit 2	Visit 3	Visit 4	Visit 5	
Maternal blood ¹	X	X	X	X	X	X
Baby(ies) blood ^{1,2}		X	X	X	X	
Breast/Chest milk ²		X	X	X	X	X
Cord blood						X
Placenta						X

¹Blood samples will be taken as peripheral blood draws, or as dried blood spot samples, as per participant preferences.

²Baby(ies) and milk samples will only be collected after delivery.

³Post-vaccination follow-up schedule will be the same for all vaccine doses (dose 1 or dose 2, if applicable).

- Visit 2 will be scheduled for ≥ 14 days after 1st dose and prior to 2nd dose
- Visit 3 will be scheduled for ≥ 14 days after 2nd dose and prior to visit 4
- Visit 4 will be scheduled for 90 days \pm 14 days after last dose
- Visit 5 will be scheduled for 180 days \pm 14 days after last dose
- If participant is getting a 2-dose vaccine, 1-month follow-up for data collection for dose 1 will occur before dose 2 administration.
- If participant is getting a 2-dose vaccine, and dose 2 scheduling is delayed (for any reason – federal/provincial/local recommendations, participant reasons), data and sample collection will be done approximately every 3 months (~120 days) until dose 2 is administered

Blood samples

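### For women who enrol after dose 1, the malformation exclusion removes anomalies first recognised between that dose and enrolment, although anomalies count in the vaccine-safety composites

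*Protocol*

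**What the plan says.** The exclusion in Protocol section 3.2.2 covers "Cases with known major fetal concerns (e.g., major congenital malformations, chromosomal abnormalities) at the time of enrollment". Its reference point is enrolment; the date of vaccination plays no part.

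Enrolment may follow the first dose. Section 3.2.1 accepts women who are "Planning to receive or have previously received one-dose of a Health Canada approved COVID-19 vaccine" in the current pregnancy, from 7 weeks 0 days with no stated upper limit of gestation. Section 3.3 requires only that recruitment comes before full vaccination. Section 3.5.4 makes the visit before dose 1 conditional and says that the baseline "questionnaire will occur at the time of enrollment prior to or during V2"; V2 falls at least 14 days after dose 1. Section 3.7.1 foresees that dose 2 may be delayed, in which case "data and sample collection will be done approximately every 3 months (~120 days) until dose 2 is administered".

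Section 3.4.2 describes the secondary outcomes as vaccine-safety outcomes. Among them is "a composite neonatal adverse outcome indicator [NAOI], which includes congenital anomalies", and the postpartum composite of paediatric complex chronic conditions has a category for congenital or genetic defects. Safety is Objective 2 in section 2.

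**The concern.** A woman vaccinated early in pregnancy whose fetus is then found to have a major malformation can no longer enter the study. The same woman with a normal scan can. For women enrolled after dose 1, part of the outcome has thus become a selection criterion that operates after exposure, and every case lost this way lowers the observed frequency. An early first dose leaves the most time for a diagnosis to fall between dose and enrolment, and Protocol section 10 promises insight into vaccine timing and safety. Women turned away at screening leave no outcome data, so later adjustment cannot recover them.

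**Working it through.** **1. Which orders of events matter.**

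| Order of events | Effect of the exclusion |
|---|---|
| Enrolment, then dose 1 | Acts only on concerns known before exposure; appropriate |
| Recognition, dose 1, enrolment | Excluded, but known before exposure; appropriate |
| Dose 1, recognition, enrolment | Excluded although recognised after exposure; this is the bias |
| Dose 1, enrolment, recognition | Enrolled and counted |

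Only the third row is at fault.

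**2. Whether another rule repairs it.** The viability requirement before first vaccination (section 3.2.1) concerns viability, not malformation. Section 4 accounts for timing of vaccination, not for timing of enrolment relative to dose 1 or to a diagnosis. No section asks for a count of women excluded under this rule.

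**3. Size.** The Protocol states no anomaly frequency and no figure for any quantity below except N, so there is nothing of its own to reproduce.

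- N = 150 (section 5).
- p = true anomaly frequency in women vaccinated in pregnancy; assumed 3%.
- f = share of women enrolled after dose 1; assumed 0.25 to 0.75.
- d = share of anomalies in that group known by enrolment; assumed 0.3 to 0.7.
- r = share of those recognitions that fall after dose 1; assumed 0.25 to 0.5.

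Share of all anomalies wrongly removed: k = f × d × r.

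| f | d | f × d (r = 1) | k at r = 0.25 | k at r = 0.5 |
|---|---|---|---|---|
| 0.25 | 0.3 | 0.075 | 0.019 | 0.038 |
| 0.5 | 0.5 | 0.25 | 0.063 | 0.125 |
| 0.75 | 0.7 | 0.525 | 0.131 | 0.263 |

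The column r = 1 (8% to 52%) is an upper illustration, because it treats every recognition before enrolment as falling after dose 1. With r between 0.25 and 0.5 the range is 2% to 26%, and the middle row gives 6% to 13%. If f = 0 or r = 0 there is no bias.

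**4. In cases.** Observed frequency = p(1 − k) / (1 − pk). Expected without the exclusion: 150 × 0.03 = 4.5.

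- k = 0.01875: 0.03 × 0.98125 / 0.99944 = 2.95%, or 4.42 cases (0.1 lost).
- k = 0.0625: 0.03 × 0.9375 / 0.99813 = 2.82%, or 4.23 cases (0.3 lost).
- k = 0.125: 0.03 × 0.875 / 0.99625 = 2.63%, or 3.95 cases (0.5 lost).
- k = 0.2625: 0.03 × 0.7375 / 0.99213 = 2.23%, or 3.35 cases (1.2 lost).

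**5. Against chance.** A Poisson count with mean 4.5 has standard deviation √4.5 = 2.1. The probability of 3 or fewer cases with no bias at all is e^(−4.5) × (1 + 4.5 + 10.125 + 15.1875) = 0.34.

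**The case against.** The strongest case on the other side is that the effect is narrow and small. Four parts of it stand.

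- The window is bounded. Enrolment must come before full vaccination, so only recognitions between dose 1 and an enrolment that itself precedes full vaccination count. A woman fully vaccinated by a single-dose product cannot enrol afterwards. A delayed dose 2 can widen the window, by an unknown amount.
- Section 3.2 describes women who intend to be vaccinated, at whatever gestation. Some will enrol before dose 1, and others will have a first dose late in pregnancy, after any scan. For both, the exclusion is proper.
- Congenital anomalies are not a stand-alone outcome. They enter through two composites whose components rest on cited sources. The dilution in the composites cannot be calculated from the Protocol.
- The primary outcome and the sample size concern immunogenicity, and no safety comparison or power is stated. About one case or fewer is at stake under the assumptions, well within chance variation.

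The denominator for safety outcomes is not stated either, and reporting by time of enrolment can be left to a statistical analysis plan. What such a plan cannot do is bring back women whom the eligibility rule has turned away.

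A reader might infer that the whole cohort's anomaly frequency will be understated by as much as half, or that the study will issue a falsely reassuring statement on malformations. The documents support neither. The first would count anomalies already known before dose 1 as losses and would take f and d at the top of assumed ranges. As to the second, the Protocol plans no separate statement on malformations.

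**Conclusion.** The point holds for women who enrol after dose 1. In that subgroup the exclusion removes anomalies first recognised between dose 1 and enrolment, and the anomaly component of both composites is biased low. The direction follows from the rule wherever such recognitions occur. Women enrolled before dose 1 are unaffected.

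The size is unknown. It equals the share of anomalies in vaccinated women that are recognised after dose 1 and before enrolment. The 2% to 26% range rests wholly on assumed f, d and r, and the case counts also on an assumed p of 3%. The relative effect on the composites is smaller still. This is a moderate design flaw in a secondary outcome. It leaves the immunogenicity objective untouched and is worth correcting because the correction is cheap.

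**What to change.** Reword the bullet in section 3.2.2 so that it excludes only major fetal concerns known before the first vaccine dose in the current pregnancy. This costs one clause.

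If eligibility is to stay as it is, report congenital anomalies, and the neonatal composite with and without them, only in women enrolled before dose 1 or before any anomaly screening result. Log each woman excluded under this bullet with the timing of dose 1 and of the diagnosis. The log has to start during recruitment, since it may not be possible to rebuild it later. The cost of this option is a smaller denominator for this outcome.

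Under either option, state the remaining limit: affected pregnancies that ended before enrolment are not captured, because enrolment requires a viable pregnancy.

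### A fetal-loss frequency pooled over all participants understates the risk from dose 1, because women who enrol after dose 1 must still have a viable pregnancy

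*Protocol*

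**What the plan says.** - **Entry after dose 1 is allowed.** Section 3.2.1 judges eligibility at enrolment and accepts women who "have previously received one-dose of a Health Canada approved COVID-19 vaccine" in the current pregnancy. Section 3.5.4 makes the pre-dose visit conditional. It also lets the baseline questionnaire, given at enrolment, be as late as Visit 2, which falls at least 14 days after dose 1.
- **Entry requires a continuing pregnancy.** Section 3.2.2 excludes "Women/Individuals with a non-viable pregnancy (e.g., ectopic", and section 3.3 says women are recruited before "they are fully vaccinated and are pregnant with a viable fetus".
- **Only one group is affected.** Section 3.2.2 also excludes "Women/Individuals who are fully vaccinated against COVID-19". Taking that term in its ordinary sense, the gap arises only with products that need a second dose.
- **Viability check.** Section 3.2.1 adds: "Documented viable pregnancy is required prior to first vaccine, to continue in the study".
- **Outcome and summary.** Section 3.4.2 lists "fetal loss/stillbirth" among the safety outcomes that serve Objective 2. Section 3.1 says the study will explore the "frequency of obstetrical and fetal/newborn outcomes; and measures of infant health and well-being". The only summary that section 4 states for categorical data is a frequency distribution. Section 4 also promises to account for the timing of vaccination but does not mention the time of enrolment.

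**The concern.** Section 3.3 defines the exposure as vaccination in pregnancy, so exposure begins at dose 1. For a woman who enrols later, the time from dose 1 to enrolment is time in which a loss could have happened but could not be observed: had it happened, she would not be in the study. This is left truncation. Pooling such women with those enrolled before dose 1, and dividing losses by all participants, gives a figure that is too low as a risk from dose 1.

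Two things are at stake. For fetal loss the error runs only towards apparent safety, and a confidence interval around the pooled frequency does not reveal it. Section 10 also promises insight into how vaccine timing bears on safety. If loss risk is higher early in pregnancy (an assumption; the protocol gives no rates), more losses go unseen among women given dose 1 early, and a comparison by timing based on pooled frequencies is distorted.

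**Working it through.** **Can other provisions recover the missing losses?**

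- The viability check in section 3.2.1 secures a viable pregnancy before the first vaccine. It says nothing about losses after that vaccine and before enrolment.
- Accounting for vaccination timing (section 4) adjusts among enrolled women. It cannot restore women who never enrolled.
- The interval need not be short. Section 3.7.1 provides for a delayed second dose, with contacts about every 120 days until it is given, and enrolment before full vaccination remains open meanwhile.

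**Size.** The protocol gives no fetal-loss rate, no share enrolling after dose 1 and no expected event count, so there is no stated figure to reproduce. Only N = 150 comes from the protocol (section 5). The rest is assumed:

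- p = 5%: risk of loss from dose 1, taken as equal in early and late enrolees
- s = 25% to 75%: share of participants enrolled after dose 1
- d = 10% to 50%: fraction of the late enrolees' loss risk that falls before enrolment

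Risk seen in late enrolees = p(1 − d)/(1 − pd). 
Pooled frequency = (1 − s)p + s × (risk seen in late enrolees).

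For s = 50%, d = 25%: 0.0375/0.9875 = 3.80%, and 0.5 × 5% + 0.5 × 3.80% = 4.40%.

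| s | d = 10% | d = 25% | d = 50% |
|---|---|---|---|
| 25% | 4.88% | 4.70% | 4.39% |
| 50% | 4.76% | 4.40% | 3.78% |
| 75% | 4.64% | 4.10% | 3.17% |

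Against 5%, the shortfall runs from 0.1 to 1.8 points (2% to 37% in relative terms). In the middle cell it is 0.6 points, or 150 × (0.0500 − 0.0440) = 0.9 of one event. It is zero if s = 0.

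**Against sampling error.** The 95% half-width of the pooled frequency is 1.96 × √(q(1 − q)/150), where q is the pooled frequency. This gives 3.4 points at q = 4.88%, 3.3 at 4.40% and 2.8 at 3.17%. The shift is smaller than the half-width in every cell.

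**What the alternatives give (s = 50%, d = 25%).**

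- *Women enrolled before dose 1 only* (n = 75): expected 5.0%, half-width 1.96 × √(0.05 × 0.95/75) = 4.9 points.
- *Delayed entry on time since dose 1*, simplified to two windows. Before enrolment, h₁ = pd = 1.25% with n₁ = 75 at risk. After enrolment, h₂ = 3.80% with n₂ = 75 × 0.9875 + 75 = 149.06 at risk. The estimate is 1 − (1 − 0.0125)(1 − 0.0380) = 5.0%. Greenwood variance = 0.95² × [0.0125/(75 × 0.9875) + 0.0380/(149.06 × 0.9620)] = 0.000391, so the half-width is 1.96 × √0.000391 = 3.9 points.

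**The case against.** **The analysis may be settled in the SAP.** No sentence prescribes a pooled frequency as the estimator for Objective 2. The frequency-distribution sentence in section 4 follows a description of the study sample, and an SAP that is not shown could use delayed entry. This stands in part: a reader might infer that the protocol commits to a wrong estimator, and it does not. What remains is fixed by the protocol. The entry rule removes these losses whatever the SAP says, and the summary the protocol names for these outcomes is a frequency.

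**The correction costs more precision than the bias it removes.** In the middle cell the root mean square error of the pooled frequency is √(0.60² + 1.67²) = 1.78 points, against a standard error of 1.98 for delayed entry. The same ordering holds in all nine cells. This stands as an argument about severity. It does not make the pooled figure a valid risk from dose 1, because the bias has a known direction and the interval does not show it.

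**Most women may enrol before dose 1.** Section 3.2 speaks of women planning to be vaccinated, and the viability check points the same way. The bias may therefore be small or nil. But section 3.2.1 expressly admits women after one dose.

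**Tempting extensions that are not supported.**

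- A reader might infer that preterm birth and the neonatal composite suffer in the same way. Dilution of preterm birth by entry at or after 37 weeks is a different mechanism, unrelated to the gap after dose 1. For the composite, which includes anomalies (section 3.2.2 excludes "Cases with known major fetal concerns (e.g., major congenital malformations, chromosomal abnormalities) at the time of enrollment"), assumed inputs move a 5% frequency only to between 4.98% and 4.71%.
- A reader might also reach for delayed entry on gestational age. That estimates cumulative loss from the earliest gestation at entry, not risk from dose 1. In a simulation on assumed weekly hazards at n = 150, its standard deviation was about 9 to 10 points, against 0.9 for the pooled frequency, because few women are at risk in the earliest weeks.

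**Conclusion.** The point holds in a limited form. By the protocol's own entry rules, fetal losses between dose 1 and enrolment are excluded among women who enrol after dose 1, so a frequency pooled over all participants understates the risk from dose 1. The direction is certain provided that someone enrols after dose 1 and some of their loss risk lies before enrolment. The numerical illustration also assumes equal risk in early and late enrolees.

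The magnitude is unknown. The illustrative shortfall of 0.1 to 1.8 points depends wholly on assumed inputs and lies within sampling error at n = 150. It would be wrong to conclude that the study's fetal-loss result will be materially misleading, or that eligibility must change. The outcome is secondary and the severity is minor.

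**What to change.** Keep eligibility unchanged and add a few sentences to section 4:

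1. Report fetal loss/stillbirth separately for women enrolled before and after dose 1.
2. Base any statement of risk from dose 1 on women enrolled before it, or on a delayed-entry estimate on the time-since-dose-1 scale with risk time starting at enrolment. For the latter, state the assumption that early and late enrolees have the same risk.
3. Describe the frequency in late enrolees as conditional on a viable pregnancy at enrolment.
4. Do not use the pooled frequency to compare safety by vaccine timing.

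In section 3.6.2, add the date or gestational age of any loss to the chart review already planned; the listed examples include gestational age at birth but not at loss. Consent date (section 3.5.3) and dose date (section 3.6.1) are already collected.

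The cost is one abstracted item, a little more analysis, and a wider interval. On the assumed inputs of the middle cell this is about ±4.9 points for the 75 women enrolled before dose 1, or ±3.9 with delayed entry, against ±3.3 pooled.
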